	Screening	Periods 1, 2, and 3					ED	Follow-up	Comments
Procedure	-28 to -3 days prior to dosing in Period 1	Day -2	Day -1	Day 1	Day 2	Day 3		At least 7 days after final dose	
Informed consent	X								
Admission to CRU		X (Period 1)	X (Periods 2&3)						
Discharge from CRU						X			
Medical history	X								
AE/medication review			X	X	X	X	X		
Height/weight	X						X	X	Height at screening only.
Neurological exam (hours)	X			Predose, 4, 8	24	48	X	X	
LY3154885/Placebo administration (hours)				0					
Vital signs (BP, PR [supine], temperature) (hours)	X		X	Predose, 2, 4, 8, 12	24, 36	48	X	X	Time points may be added for each study period, if clinically indicated. On Day 1, temperature will be measured at predose only.
ABPM			X	X	X				The ABPM on Day -1 is a 24-hour collection in Period 1 only (baseline measurement). See Section 9.4.4.
Clinical laboratory tests	X	X		Predose		X	X	X	See Appendix 2, Clinical Laboratory Tests, for details. PI must review the result of Day-2 results prior to Day 1 dose in Period 1 only.
Pregnancy test	X	X					X	X	Serum test at screening and admission of Period 1 only; urine test at all other time points.
PE/MA	X			Predose			X	X	Full PE/MA at screening and prior to final discharge from the study. Symptom-directed PE/MA at all other time points and as deemed necessary by the investigator.

continued

Study Schedule Protocol J1Z-MC-HUAA (Part A: Single-Ascending Dose – 3 Study Periods) (concluded)

	Screening	Periods 1, 2, and 3					ED	Follow-up	Comments
Procedure	-28 to -3 days prior to Period 1	Day -2	Day -1	Day 1	Day 2	Day 3		At least 7 days after final dose	
Single safety 12-lead ECG (hours)	X			Predose, 2, 4	24	48	X	X	
PK sampling (hours)				Predose, 0.5, 1, 2, 3, 4, 5, 6, 8, 12	24, 36	48			Sampling times are relative to the time of study treatment administration (0 hour).
Stored non-PGx plasma sample (hours)				Predose, 8	24				Stored sample for biomarker research. Sampling times are relative to the time of study treatment administration (0 hour).
PGx sample			X						Single sample for pharmacogenetic analysis taken prior to/on Day 1 of Period 1.
Urine collection (hours)				0-12, 12-24	24-36				Urine collection time starts from actual dosing time on Day 1 and finishes within \pm 30 minutes of the 36-hour time point.
Serum creatinine				Predose					To be collected at predose and sent to central laboratory.

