Pregnancy test				X	X	Serum test at screening and admission; urine test at all other time points. Women with confirmed nonchildbearing potential status can be exempted from further pregnancy tests during the study after screening.
Neurological exam (hours) ^a	48					The 8-hour time point is optional.
Clinical laboratory tests			X	X	X	See Appendix 2 , Clinical Laboratory Tests, for details. PI must review the Day -2 laboratory result before dosing on Day 1
ABPM	X					The ABPM on Day -1 is a 24-hour collection for baseline measurement. On dosing days, the ABPM recording will be initiated approximately 2 hours prior to dosing for measurement of predose baseline.
Administration of itraconazole	X	X				Itraconazole 200 mg will be administered twice daily on Day 8 (dose separated by 12 hours) and once daily on Days 9 through 17. Itraconazole should be administered at approximately the same time every morning. For the outpatient dosing days, subjects will record the actual time of dose administration on a diary card. On Day 14, itraconazole should be administered 1 hour before LY3154885 administration (see Section 5.1.2).
Vital signs (BP, PR [supine], temperature) (hours) ^a	48, 60	72	96	X	X	Time points may be added for each study period, if clinically indicated. On Day 1, temperature will be measured at predose only.
12-lead ECG			X	X	X	Single safety ECGs.
PGx Sample						Single sample for pharmacogenetic analysis.
LY3154885 PK sampling (hours) ^a	48, 60	72	96			Sampling times are relative to the time of LY3154885 administration (0 hour).

Note: Site should schedule activities as appropriate. In cases where several study procedures are scheduled at the same time, follow this order of priority for procedures: ECG, vital signs, PK samples, and clinical laboratory tests.

Abbreviations: ABPM = ambulatory blood pressure monitoring; AE = adverse event; BP = blood pressure; CRU = clinical research unit; CYP = cytochrome P450; ECG = electrocardiogram; ED = early discontinuation; MA = medical assessment; PE = physical examination; PI = principal investigator; PK = pharmacokinetic; PR = pulse rate.

a Predose time points refer to dosing before itraconazole and LY3154885. All postdose time points are relative to the LY3154885 dose.

Study Schedule Protocol J1Z-MC-HUAA (Part C: Multiple-Ascending Dose – Single Period)

	Screening	Days										ED	Follow-up	Comments
Procedure	-28 to -3	-2	-1	1	2	3-6	7	8-13	14	15		Approx 7 days after discharge		

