Informed consent	X													
Admission to CRU		X				D6		D10					Afternoon admission.	
Discharge from CRU						D3		D8		X				
Medical history	X													
AE/medication review			X	X	X	X	X	X	X	X	X			
Height/weight	X		X							X			Height at screening only.	
Neurological exam (hours)	X			Predose, 4, (8)	24	48	Predose, 4, (8)	24, 48		X	X		The 8-hour time point is optional.	
LY3154885/Placebo administration				X	X	X	X	X					On Days 4, 5, 6, 9, and 10, subjects will receive their dose of LY3154885/placebo at the CRU and then may be discharged at the discretion of the investigator.	
Vital signs (BP, PR [supine], temperature) (hours)	X		X	Predose, 2, 4, 8, 12	Predose, 2, 4, 8, 12	Predose, 2	Predose, 2, 4, 8, 12	Predose, 2	Predose, 2, 4, 8, 12	X	X	X	Time points on outpatient dosing days (Days 4, 5, 6, 9, and 10) may be adjusted based on emerging data from Part A and/or if clinically indicated. On Days 1 to 14, temperature will be measured at predose only.	

continued

Study Schedule Protocol J1Z-MC-HUAA (Part C: Multiple-Ascending Dose – Single Period) (continued)

Procedure	Screening	Days										ED	Follow-up	Comments
		-28 to -3	-2	-1	1	2	3-6	7	8-13	14	15			
ABPM			X	X	X		X	D11&12	X					The ABPM on Day -1 is a 24-hour collection for baseline measurement. On dosing days, the ABPM recording will be initiated approximately 2 hours prior to dosing for measurement of predose baseline.
Clinical laboratory tests	X	X		Predose			Predose			X	X	X		See Appendix 2 , Clinical Laboratory Tests, for details. PI must review Day -2 result prior to dose on Day 1.
Pregnancy test	X	X					Predose			X	X	X		Serum test at screening and admission; urine test at all other time points per investigator discretion. Women with confirmed nonchildbearing potential status can be exempted from further pregnancy tests during the study after screening.
PE/MA	X			Predose						X	X	X		Full PE/MA at screening and prior to final discharge from the study. Symptom-directed PE/MA at all other time points and as deemed necessary by the investigator.

continued

Study Schedule Protocol J1Z-MC-HUAA (Part C: Multiple-Ascending Dose – Single Period) (concluded)

	Screening	Days										ED	Follow-up	Comments
Procedure	-28 to -3	-2	-1	1	2	3-6	7	8-13	14	15		Approx 7 days after discharge		

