8.3. Subjects Lost to Follow-up

A subject will be considered lost to follow-up if he or she repeatedly fails to return for scheduled visits and is unable to be contacted by the study site. Site personnel are expected to make diligent attempts to contact subjects who fail to return for a scheduled visit or were otherwise unable to be followed up by the site.

9. Study Assessments and Procedures

Section 2 lists the Schedule of Activities, detailing the study procedures and their timing (including tolerance limits for timing).

The specifications in this protocol for the timing of safety and sample collection are given as targets to be achieved within reasonable limits. Modifications may be made to the time points based upon emerging clinical information. The scheduled time points may be subject to minor alterations; however, the actual procedure time has to be correctly recorded in the CRF, including samples that are collected outside of the allowable time window. Failure or being late (ie, outside stipulated time allowances) to perform procedures or obtain samples due to legitimate clinical issues (eg, equipment technical problems, venous access difficulty, or subject defaulting or turning up late on an agreed scheduled procedure) will not be considered as protocol deviations but the CRU will still be required to notify the sponsor in writing via a file note.

[Appendix 2](#) lists the laboratory tests that will be performed for this study.

[Appendix 5](#) provides a summary of the maximum number and volume of invasive samples, for all sampling, during the study.

Unless otherwise stated in the subsections below, all samples collected for specified laboratory tests will be destroyed within 60 days of receipt of confirmed test results. Certain samples may be retained for a longer period, if necessary, to comply with applicable laws, regulations, or laboratory certification standards.

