9.5. Pharmacokinetics

At the visits and times specified in the Schedule of Activities (Section 2), venous blood samples of approximately 3 mL and approximately 2 mL will be collected to determine the plasma concentrations of LY3154885 and itraconazole, respectively. If indicated by emerging data, a maximum of 3 blood samples per subject may be collected at additional time points during the study if warranted and agreed upon between both the investigator and sponsor. Instructions for the collection and handling of blood samples will be provided by the sponsor. The actual date and time (24-hour clock time) of each sampling will be recorded.

Drug concentration information that may unblind the study will not be reported to investigative sites or blinded personnel until the study has been unblinded.

Urine samples will be collected for the characterization of renal clearance of LY3154885. Urine samples will be used to determine creatinine and LY3154885 concentration. Total urine output for the appropriate period post LY3154885 administration will be collected, pooled, and refrigerated. At the end of the collection period, the total urine volume will be recorded. Any special instructions for the collection and handling of urine samples will be provided by the sponsor. Exploratory metabolite identification of LY3154885 may be conducted using urine samples. In Part A only, venous blood samples of approximately 3.5 mL each will be collected to determine serum creatinine measurements.

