9.7. Genetics

A blood sample will be collected for pharmacogenetic analysis as specified in the Schedule of Activities (Section 2), where local regulations allow.

Samples will not be used to conduct unspecified disease or population genetic research either now or in the future. Samples will be used to investigate variable exposure or response to LY3154885 and to investigate genetic variants thought to play a role in neurodegenerative diseases or neurological disorders. Assessment of variable response may include evaluation of AEs or differences in efficacy.

All samples will be coded with the subject number. These samples and any data generated can be linked back to the subject only by the investigative site personnel.

Samples will be retained for a maximum of 15 years after the last subject visit, or for a shorter period if local regulations and/or ERBs/IRBs impose shorter time limits, for the study at a facility selected by Lilly. This retention period enables use of new technologies, response to regulatory questions, and investigation of variable response that may not be observed until later in the development of LY3154885 or after LY3154885 is commercially available.

Molecular technologies are expected to improve during the 15-year storage period and therefore cannot be specifically named. Regardless of technology utilized, data generated will be used only for the specific research scope described in this section.

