Appendix 5. Blood Sampling Summary

This table summarizes the approximate number of venipunctures and blood volumes for all blood sampling (screening, safety laboratories, and bioanalytical assays) during the study.

Protocol J1Z-MC-HUAA Sampling Summary (Part A: Ascending Dose—3 Study Periods)

Purpose	Blood Volume per Sample (mL)	Number of Blood Samples	Total Volume (mL)
Screening tests ^a	18	1	18
Clinical laboratory tests ^a	8	7	56
PK sampling ^b	2	39 (+3)	78 (+6)
Blood discard for cannula patency	1	30	30
Stored non-PGx plasma sample	10	9	90
PGx sample	10	1	10
Serum creatinine	3.5	3	10.5
Total			292.5 (298.5)
Total for clinical purposes (rounded up to nearest 10 mL)			300 (300)

Abbreviations: PGx = pharmacogenetic; PK = pharmacokinetic.

a Additional samples may be drawn if needed for safety purposes.

b If indicated by emerging data, a maximum of 3 blood samples may be collected at additional time points during the study if warranted and agreed upon between both the investigator and sponsor (as shown in parentheses).

Protocol J1Z-MC-HUAA Sampling Summary (Part B: CYP3A4 Inhibition—Single Study Period)

Purpose	Blood Volume per Sample (mL)	Number of Blood Samples	Total Volume (mL)
Screening tests ^a	18	1	18
Clinical laboratory tests ^a	8	5	40
PK sampling for LY3154885 ^b	2	29 (+3)	58 (+6)
PK sampling for itraconazole and metabolite(s)	2	7	14
Blood discard for cannula patency	1	20	20
Total			150 (156)
Total for clinical purposes (rounded up to nearest 10 mL)			150 (160)

Abbreviation: PK = pharmacokinetic.

a Additional samples may be drawn if needed for safety purposes.

b If indicated by emerging data, a maximum of 3 blood samples may be collected at additional time points during the study if warranted and agreed upon between both the investigator and sponsor (as shown in parentheses).

Protocol J1Z-MC-HUAA Sampling Summary (Part C: Multiple-Ascending Dose—Single Study Period)

Purpose	Blood Volume per Sample (mL)	Number of Blood Samples	Total Volume (mL)
Screening tests ^a	18	1	18
Clinical laboratory tests ^a	8	4	32
PK sampling ^b	2	33 (+3)	66 (+6)
Blood discard for cannula patency	1	30	30
Stored non-PGx plasma sample	10	5	50
PGx sample	10	1	10
Total			206 (212)
Total for clinical purposes (rounded up to nearest 10 mL)			210 (220)

Abbreviations: PGx = pharmacogenetic; PK = pharmacokinetic.

a Additional samples may be drawn if needed for safety purposes.

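### Appendix 5 omits scheduled blood draws in Parts A to C and costs LY3154885 PK samples at 2 mL where Section 9.5 says 3 mL

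*Protocol*

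**What the plan says.** **Volume per sample.** Protocol Section 9.5 says that "venous blood samples of approximately 3 mL and approximately 2 mL will be collected to determine the plasma concentrations of LY3154885 and itraconazole, respectively". In Appendix 5, the LY3154885 PK row of every table (Parts A, B, C and D) uses 2 mL.

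**Status of Appendix 5.** The opening of Section 9 says that the appendix "provides a summary of the maximum number and volume of invasive samples, for all sampling, during the study". The appendix introduces itself differently: "This table summarizes the approximate number of venipunctures and blood volumes for all blood sampling".

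**Day -2 laboratory sample.** The Schedule of Activities (Section 2) marks clinical laboratory tests on Day -2 in Parts A, B and C. The comments are:
- Part A: "PI must review the result of Day-2 results prior to Day 1 dose in Period 1 only"
- Part B: "PI must review the Day -2 laboratory result before dosing on Day 1"
- Part C: "PI must review Day -2 result prior to dose on Day 1"

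**Pharmacogenetic (PGx) sample.** Section 9.7 says: "A blood sample will be collected for pharmacogenetic analysis as specified in the Schedule of Activities". The Part B schedule places this sample on Day 1. The Appendix 5 tables for Parts A, C and D each have a PGx row of one 10 mL sample. The Part B table has none.

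**The concern.** There are two separate faults, and mending one does not mend the other.

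First, the volume to draw for the main assay differs by half between the section that instructs collection and the table that adds it up. Of the volumes given in Section 9.5, itraconazole (2 mL) and serum creatinine (3.5 mL) agree with Appendix 5. Only LY3154885 does not.

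Second, whichever volume is right, the tables for Parts A to C count fewer draws than the schedule requires.

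At stake is the accuracy of the blood burden stated for healthy volunteers, for whom Section 3.3 expects no therapeutic benefit, and a single collection volume for the site. No endpoint, analysis or sample size depends on it.

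**Working it through.** **1. Reproduce the printed totals** (volume × number, summed over the rows of Appendix 5, in mL)

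- A: 18 + 56 + 78 + 30 + 90 + 10 + 10.5 = 292.5
- B: 18 + 40 + 58 + 14 + 20 = 150
- C: 18 + 32 + 66 + 30 + 50 + 10 = 206
- D: 18 + 128 + 234 + 90 + 10 = 480

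The three optional PK samples at 2 mL add 6, giving 298.5, 156, 212 and 486. All eight figures match the print, so the addition is sound and the fault lies in the inputs.

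**2. Rebuild the counts from the Schedule of Activities** for a subject who completes (no early-discontinuation visit). Screening has its own row and is left out here.

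PK samples for LY3154885:
- A: 13 per period × 3 = 39
- B: 13 after Day 1 + 16 after Day 14 = 29
- C: 10 + 1 + 10 + 1 + 10 + 1 = 33
- D: 13 × 9 = 117

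All four agree with Appendix 5.

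Clinical laboratory draws:

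| Part | Scheduled draws | Count | Appendix 5 |
|---|---|---|---|
| A | Day -2 (Period 1), 3 predose, 3 on Day 3, follow-up | 8 | 7 |
| B | Days -2, 1, 8, 14, 18, follow-up | 6 | 5 |
| C | Days -2, 1, 7, 15, follow-up | 5 | 4 |
| D | 5 per period × 3, follow-up | 16 | 16 |

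Parts A, B and C are each one short, which is the Day -2 draw. That draw does not replace the Day 1 predose sample: the schedule lists both, and SAP Section 9.5.3 takes Day 1 predose as the laboratory baseline. The exact match in Part D and in all PK counts indicates that this is the counting method the appendix itself uses.

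**3. Volume of the missing draws**

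- A: 1 × 8 = 8 mL
- B: 1 × 8 + 10 (PGx, assumed volume) = 18 mL
- C: 1 × 8 = 8 mL
- D: 0 mL

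**4. Effect of 3 mL instead of 2 mL:** 1 mL per PK sample, so +39, +29, +33 and +117 mL.

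**5. Corrected totals** (in brackets: with the three optional samples, +6 at 2 mL or +9 at 3 mL)

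| Part | Stated | At 2 mL | Low by | At 3 mL | Low by |
|---|---|---|---|---|---|
| A | 292.5 (298.5) | 300.5 (306.5) | 8 (2.7%) | 339.5 (348.5) | 47 (16.1%) |
| B | 150 (156) | 168 (174) | 18 (12.0%) | 197 (206) | 47 (31.3%) |
| C | 206 (212) | 214 (220) | 8 (3.9%) | 247 (256) | 41 (19.9%) |
| D | 480 (486) | 480 (486) | 0 | 597 (606) | 117 (24.4%) |

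Percentages are of the stated base total. With the optional samples included, the shortfall is unchanged at 2 mL and becomes 50, 50, 44 and 120 mL at 3 mL.

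**6. Sensitivity to two readings**

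- Part B without the assumed 10 mL: 158 mL (2 mL) or 187 mL (3 mL), low by 8 or 37 mL, plus whatever the PGx sample takes.
- Part A if Day -2 laboratory tests were drawn in all three periods: 3 × 8 = 24 mL low at 2 mL, or 24 + 39 = 63 mL low at 3 mL.

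**The case against.** The best case for leaving this alone is that it is small and the table does not claim precision. Appendix 5 calls its figures approximate, Section 9.5 hedges its volumes too, and a footnote allows extra safety samples. At 2 mL, Parts A and C are only 8 mL low. The larger figures depend on 3 mL being right, which the documents do not establish. No per-subject limit on blood volume is set. The nearest figure is the 450 mL donation threshold in exclusion criterion 26, which governs entry, not conduct. Corrected Parts A to C stay below it at either volume, and Part D exceeds it as printed.

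Much of this stands as to weight: it is a documentation correction. It does not remove the fault. Section 9 describes the appendix as a maximum, and a maximum below what the schedule requires is wrong. The footnote covers samples that turn out to be necessary, not a routine draw whose result must be reviewed before Day 1 dosing. A 50% difference repeated over 29 to 117 samples is not approximation.

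Three points of detail also deserve stating:
- The Part B PGx volume is assumed, and Section 9.7 makes collection subject to local rules.
- The Part A comment limits the investigator's review to Period 1, not expressly the draw. The one-draw reading rests on Day -2 admission being for Period 1 only.
- Part D calls for a serum pregnancy test at Period 1 admission, with no row and no volume in Appendix 5. It can be waived once nonchildbearing status is confirmed, and only such women are eligible, so it is not counted here. The zero for Part D at 2 mL therefore refers to the laboratory, PK and PGx rows.

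**Conclusion.** The concern holds. Section 9.5 and Appendix 5 conflict on the LY3154885 sample volume. Independently, the Appendix 5 tables for Parts A, B and C omit scheduled draws. The A/B/C/D totals are low by 8/18/8/0 mL if 2 mL applies and by 47/47/41/117 mL if 3 mL applies. Part D is wrong only in the second case.

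These figures assume a completer, one Day -2 laboratory draw in Part A, and 10 mL for the Part B PGx sample. The documents do not show which PK volume is intended, and this review does not choose between them.

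The correction should be made, but it touches only the stated blood burden and the collection instruction. A likely origin for Parts B and C is that the amendment (b) summary reports adding Day -2 laboratory tests there and lists no change to Appendix 5.

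**What to change.** 1. Reconcile the LY3154885 PK sample volume between Section 9.5 and Appendix 5.
2. Whichever volume is confirmed, add the Day -2 laboratory sample to the Part A, B and C tables, and a PGx row with its actual volume to the Part B table.
3. Restate the totals and the totals rounded up to 10 mL. On the assumptions above, the rounded totals (with optional samples in brackets) become:

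| Part | Stated | At 2 mL | At 3 mL |
|---|---|---|---|
| A | 300 (300) | 310 (310) | 340 (350) |
| B | 150 (160) | 170 (180) | 200 (210) |
| C | 210 (220) | 220 (220) | 250 (260) |
| D | 480 (490) | 480 (490) | 600 (610) |

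The cost is corrected tables for Parts A to C in either case. If 2 mL is confirmed, one number in Section 9.5 also changes. If 3 mL is confirmed, the PK rows of all four tables change. Correcting Section 9.5 alone would leave Parts A to C wrong. The stated blood volumes become less favourable for Parts A to C either way, and for Part D as well at 3 mL.

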9.5.1. Bioanalysis

Samples will be analyzed at a laboratory approved by the sponsor and stored at a facility designated by the sponsor.

Concentrations of LY3154885 and itraconazole and metabolites will be assayed using a validated liquid chromatography with tandem mass spectrometry (LC/MS/MS) method. Samples collected from subjects receiving placebo will be retained and only analyzed for LY3154885 if required to confirm subject dosing records.

Bioanalytical samples collected to measure investigational product concentrations (including placebo samples) will be retained for a maximum of 2 years following last subject visit for the study. During this time, samples remaining after the bioanalyses may be used for exploratory analyses, such as metabolism and/or protein binding work.

9.6. Exploratory Pharmacodynamics

9.6.1. *Exploratory Cognition Assessments (Part C Only)*

The Digital Symbol Substitution Test (DSST) and Hopkins Verbal Learning Test (HVLT) will be included in Part C to assess relevant aspects of cognition, vigilance, and working memory that may provide a pharmacodynamic signal in healthy volunteers. The tests will be completed at the time points stipulated in the Schedule of Activities (Section 2).

- *DSST*: The DSST is an assessment of complex scanning and visual tracking. The screen shows a series of 9 numbered symbols that represent a “key.” The participant is then presented with a series of parallel boxes that contain a symbol in the top half of the box and must provide a “number” response for the bottom half by referring to the key. Numbers are selected using the touch screen. The participant is given 90 seconds to respond to as many symbols as possible.
- *HVLT*: The HVLT is an easily administered 12-item, 3 learning trial, verbal learning test with delayed recall and recognition memory testing. The test requires recall of a series of 12 words over 3 learning trials, free recall after a delay, and a recognition trial.

